5.8.3 Premature Discontinuation of Study Treatment (Transition to “Reduced Follow- up” Treatment)

Study treatment will begin at the time of the first dose of induction antibody therapy for an islet transplant. Study treatment may be prematurely discontinued for any subject for any of the following reasons:

- The subject is unwilling or unable to comply with the protocol.
- The investigator believes that the study treatment is no longer in the best interest of the subject.
- The renal allograft is lost and the subject elects to terminate chronic immunosuppression.
- Graft Failure: See Study Definitions and Section 5.8.2.
- An unexpected related SAE. The agent(s) to which the event is attributed will be discontinued.

Subjects who prematurely discontinue study treatment will remain in the study until normal termination, for the purpose of monitoring safety and efficacy parameters and will enter the reduced follow-up schedule outlined in Appendix 2. Data from these subjects will be used in the intent-to-treat analysis.

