8.2 Adverse Events

8.2.1 Collecting Procedure

Only AEs that are associated with a protocol mandated procedure, which is not part of the normal standard of care for the subject, and severe hypoglycemic events (see study definitions), will be collected after the screening consent has been obtained and until the subject initiates standard diabetes care or is placed on the wait list (whichever comes first). All AEs will be collected from at the time the subject initiates study-directed diabetes care or is placed on the protocol waitlist (whichever comes first) until study completion, or for 30 days after the subject prematurely withdraws from the study. AEs will be followed until the time the event is resolved, stabilized, or the subject completes or withdraws from the study, whichever comes first.

AEs may be discovered through any of these methods:

- Observing the subject.
- Questioning the subject, which should be done in an objective manner.
- Receiving an unsolicited complaint from the subject.
- An abnormal value or result from a clinical or laboratory evaluation (e.g., a radiograph, an ultrasound, or an ECG) can also indicate an AE. If this is the case, then the evaluation that produced the value or result should be repeated until the value or result returns to normal or can be explained and the subject's safety is not at risk. If an abnormal value or result is determined by the investigator to be clinically significant, it must be reported as an AE.

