8.2.2 Recording Procedure

Throughout the study, the investigator will record all AEs on the appropriate AE CRF regardless of their severity or relation to study medication or study procedure. The investigator will treat subjects experiencing AEs appropriately and observe them at suitable intervals until their symptoms resolve or their status stabilizes.

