10.1.3 Exploratory Endpoints

Exploring novel approaches to monitoring islet graft injury will serve as the basis for hypotheses generation in future trials. We will calculate descriptive statistics for the safety and efficacy of the new approaches. Adverse events rates will be tabulated and 95% confidence intervals (CI) will be calculated. We will calculate the mean, median, minimum, maximum, inter-quartile ranges, and 95% CI of loss of engrafted islets estimated by early post infusion release of insulin specific DNA, TAT and C3a. Success rate and 95% CI will be estimated.

Other secondary and exploratory endpoints include relative functional engrafted islet mass, the proportion achieving insulin independence, the proportion achieving HbA1c \leq 6.5% and an absence of severe hypoglycemic events, the proportion achieving HbA1c $<$ 7.0%, reduction in HbA1c of at least 1 point, the change in Clarke score, c-peptide, Glycemic lability index (LI), glucose and glucose variability. These endpoints will also be analyzed using descriptive statistics.

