APPENDIX 1: Sequence of Events

Time points (days relative to transplant)	S C R E N	WL ¹	BL ²	D ³	D ³	W ¹	W ²	W ³	W ⁴	M ²	M ^{2½}	M ⁶	M ⁹	M ¹²	365 post-initial Tx	Year 2				730 post-initial Tx
		1	2	3	4	5	6	7	8	9	10	11	12	13	14	Y1	15	16	17	18
Visit #	1	2	3	4	5	6	7	8	9	10	11	12	13	14	Y1	15	16	17	18	Y2
Visit Windows (specified in days)	N/A	N/A	≤ 2	N/A	N/A	± 3				± 10	± 5	± 7	±14				± 90			
Informed Consent	X																			
Medical and Diabetes History	X																			
Inclusion / Exclusion	X		X																	
Retinopathy Exam	X	X-yrly																		
Radiologic Exams																				
ECG	X	X-yrly	X													X				X
Chest X-Ray ⁷	X		X																	
Abdominal US (or MRI if clinically indicated)	X					X ⁵														
Cardiac Persantine thallium or Stress echo or equivalent	X																			
General Assessments																				
Physical Exam ⁶	X	X-yrly	X ⁶	X	X	X	X	X	X	X	X	X	X	X	X	X	X	X	X	X
Review Medications ⁸	X	X	X	X	X	X	X	X	X	X	X	X	X	X	X	X	X	X	X	X
AE/Hypo. Events		X	X	X	X	X	X	X	X	X	X	X	X	X	X	X	X	X	X	X
Clarke Score	X	X-q6Mo										X			X	X				X

Time points (days relative to transplant)	S C R E E N	WL ¹	BL ²	D ^{0³}	D ₃	D ₇	W ₁	W ₂	W ₃	W ₄	M ₂	M _{2½}	M ₆	M ₉	M ₁₂	365 post-initial Tx	Year 2				730 post-initial Tx
																	M ₁₅	M ₁₈	M ₂₁	M ₂₄	
Visit #	1	2	3	4	5	6	7	8	9	10	11	12	13	14	Y1	15	16	17	18	Y2	
Visit Windows (specified in days)	N/A	N/A	≤ 2	N/A	N/A		± 3				± 10	± 5	± 7	± 14						± 90	
Local Laboratory Assessments																					
CBC w/ Diff	X	X-q6mo	X	X ¹⁰	X	X	X	X	X	X	X	X	X	X	X	X	X	X	X	X	
Comprehensive Metabolic Panel ¹¹	X	X-q6mo	X	X ¹⁰	X	X	X	X	X	X-q1mo ¹²						X	X	X	X	X	
Calcineurin levels	X	X-q6mo	X	X	X	X	X	X	X	X	X	X	X	X	X	X	X	X	X	X	
PRA by Luminex ⁴	X	X-qMo														X	X			X	X
Coagulation (PT, PTT, INR)	X		X																		
Pregnancy test (females) ¹³	X		X																		
Serology (HBV, HCV, HIV) ⁹	X	X-yrly														X	X			X	
Fasting Lipids (TG, TC, HDL, LDL)	X	X-q6mo														X	X			X	
Apolipoprotein A1 & B, C-Reactive Protein		X														X	X			X	
T-Spot TB Test (or equivalent)	X	X-yrly														X				X	
AAT Levels ²⁶ (Send out to Quest Diagnositcs)								X													
Immunoglobulin A (IgA)	X																				
Urinalysis	X																				
Blood type/HLA	X ²¹		X																		

Time points (days relative to transplant)	S C R E E N	WL ¹	BL ²	D ³ 0	D ³	D ⁷	W ¹ 14	W ² 21	W ³ 28	W ⁴	M ² 56	M ^{2 1/2} 75	M ⁶ 180	M ⁹ 270	M ¹² 365	365 post-initial Tx	Year 2				730 post-initial Tx

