APPENDIX 2: Reduced Follow-up Schedule of Events

Subjects prematurely discontinued from study treatment according to the criteria previously stated will remain in the study until normal termination. For the purpose of monitoring safety and efficacy parameters, the subjects should be followed according to the reduced follow-up schedule. The day on which the study treatment is discontinued is considered "Day 0". The last reduced follow-up visit will vary depending on when the subject discontinues study treatment and should be done at 3 years after the subject's final transplant.

Days post-discontinuation of study treatment	28	56	75	180	270	365	1 year post- final	2 years post- final	3 years post- final
Visit Windows (specified in days)	± 7						± 14		
Equivalent Month	1	2	2.5	6	9	12	Varies	Varies	Varies
ASSESSMENTS FOR ALL SUBJECTS ON REDUCED FOLLOW-UP									
Assess SAEs and hypoglycemic events ¹	X	X	X	X	X	X	X	X	X
Alloantibody (central)				X			X	X	X
HbA1c (central)							X	X	X
SCr (central)							X	X	X
QOL questionnaires via mail							X	X	X

1: If subject does not come to the study site for the visit, attempt to obtain information via a phone contact.

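### Sections 8.2.1 and 8.2.2 require all adverse events to study completion, but Appendix 2 schedules only serious and hypoglycemic events for subjects on reduced follow-up, and the AE rate has no defined denominator

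*Combined protocol and SAP*

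**What the plan says.** Section 8.2.1 sets the collection period: "All AEs will be collected from at the time the subject initiates study-directed diabetes care or is placed on the protocol waitlist", whichever is earlier, "until study completion, or for 30 days after the subject prematurely withdraws from the study". Section 8.2.2 adds: "Throughout the study, the investigator will record all AEs on the appropriate AE CRF regardless of their severity". The main schedule in Appendix 1 matches this, with a row labeled "AE/Hypo. Events" running through the post-transplant visits.

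Section 5.8.3 says that subjects who stop study treatment early "will remain in the study until normal termination, for the purpose of monitoring safety and efficacy parameters and will enter the reduced follow-up schedule". They have not withdrawn, so the 30-day limit in 8.2.1 does not apply to them. The safety row of their schedule in Appendix 2 reads "Assess SAEs and hypoglycemic events", with telephone contact allowed if the subject does not attend. There is no row for other adverse events.

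The only sentence on AE rates in section 10 is in 10.1.3: "Adverse events rates will be tabulated and 95% confidence intervals (CI) will be calculated". It does not say which events count, over what period, or per what denominator.

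**The concern.** The two instructions cannot both be followed. A site that works from Appendix 2 stops asking about non-serious events; a site that works from section 8 continues. Ascertainment could therefore differ between sites, and between subjects within a site.

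The affected group is not a random sample. The routes in section 5.8.3 include graft failure, renal graft loss with a choice to end immunosuppression, non-compliance, the investigator's judgment about the subject's best interest, and an unexpected related SAE. Section 5.8.2 specifies that a subject with graft failure moves once it is settled that no further islet transplant will follow. Section 7.6 adds anyone who does not meet the criteria for another transplant. Non-serious events would thus go unrecorded in a group selected largely by how the transplant turned out.

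An analyst who divided all recorded events by all follow-up would treat the restricted period as fully observed. With 20 transplanted subjects, a few moves can noticeably change the safety summary.

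**Working it through.** **Does any text resolve the conflict?**

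| Point | Sections 8.2.1, 8.2.2 and Appendix 1 | Appendix 2 |
|---|---|---|
| Events | All, any severity | SAEs and hypoglycemic events |
| End | Study completion, or 30 days after withdrawal | Three years after the final transplant |
| Subject's status | In the study | In the study (5.8.3) |

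Neither side refers to the other as an exception, and no other section sets an order of precedence. SAE collection (8.3.1) runs from consent to 30 days after completion or withdrawal, so Appendix 2 does not change it.

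**How large could the gap be?** The plan gives no AE rate and no expected number of moves, so there is no figure to reproduce. What follows is an illustration.

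Inputs from the documents: 20 transplanted subjects (10.3.1); at least 36 months of follow-up after the last transplant (7.5); no further transplant after month 8 (7.6.2).

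Assumptions: Appendix 2 governs; each subject has one transplant, so both clocks start together; a fraction f moves at month 8; the true AE rate is constant; a fraction s of all AEs are serious or hypoglycemic and still captured.

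Share of follow-up without non-serious capture = f × (36 − 8)/36 = f × 0.778. Observed/true rate for all AEs per person-time = 1 − share × (1 − s). Total follow-up is 20 × 36 = 720 subject-months.

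| f | Restricted subject-months | Share | Observed/true, s = 0.1 to 0.4 |
|---|---|---|---|
| 10% | 2 × 28 = 56 | 7.8% | 93% to 95% |
| 25% | 5 × 28 = 140 | 19.4% | 83% to 88% |
| 50% | 10 × 28 = 280 | 38.9% | 65% to 77% |

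Sensitivity to the assumptions:

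- With a move at day 75 (2.5 months), the shares are 9.3%, 23.3% and 46.5%.
- With 24 months of follow-up, close to the last Appendix 1 column at day 730, the factor is (24 − 8)/24 = 0.667. Then 10% and 50% moving give 6.7% and 33.3%.
- If section 7.6 is read literally together with the month-8 limit, every subject moves. The share is 77.8% and the observed rate is 30% to 53% of the true rate.

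**Does the type of rate matter?** Suppose the rate is the proportion with at least one AE. Under a Poisson process with r events per month, a subject who moves at month 8 has probability 1 − exp(−36r) under full capture and 1 − exp(−8r − 28rs) under Appendix 2. Take s = 0.2:

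- r = 0.1: 1 − exp(−3.6) = 97.3% falls to 1 − exp(−1.36) = 74.3%.
- r = 0.5: 1 − exp(−18) = 100.0% falls to 1 − exp(−6.8) = 99.9%.

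So this proportion hardly moves when events are frequent, but falls clearly in the affected subjects when they are infrequent. The effect on the whole cohort is f times as large.

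**The case against.** The strongest reply is that Appendix 2 is a visit schedule and nothing says it overrides section 8. Section 8.2.1 also counts unsolicited complaints as a way of learning of an event. If section 8 governs, nothing is lost by rule. That is correct. What remains is that a site cannot tell which text to follow. In addition, Appendix 2 drops the physical examination, blood count and metabolic panel, although 8.2.1 lists abnormal results as another way to find events.

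A second reply is that the 10.1.3 sentence sits among exploratory endpoints, after text on new ways of monitoring graft injury, and may not describe a trial-wide AE table. This is a fair reading. It means that section 10 may contain no general AE analysis at all, which is a further reason to define one.

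A reader might infer that AE rates must fall over time and after graft failure by construction, and that any observed decline is only a change of form. The documents do not support this. It requires that Appendix 2 governs and that a person-time rate is used, and neither is stated; no AE trend is planned. Some real decline is also plausible. ATG ends on day +2, etanercept on day +10, AAT after three weeks and valganciclovir after 14 weeks, so a move at month 8 leaves these first-transplant exposures under full capture. If events cluster early, the loss is smaller than the constant-rate figures. Graft failure alone does not trigger the move, and intolerance of medication is not itself a listed reason. Nor do the documents show that subjects who move are those most prone to adverse events.

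The consequences are also bounded. The primary endpoint is untouched, and the specific suspension triggers in section 6.2 rest on fatal or life-threatening events, primary non-function, c-peptide and procedure-related SAEs.

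**Conclusion.** The contradiction between sections 8.2.1 and 8.2.2 and Appendix 2 is real, and no text resolves it. If Appendix 2 is followed, non-serious capture stops in an outcome-related subset, and a person-time AE rate over all follow-up is too low. The amount cannot be derived from the documents. The illustrative 8% to 39% of follow-up rests on 10% to 50% of subjects moving at month 8 of 36. The resulting rate bias also depends on the assumed constant AE rate and on the mix of serious and non-serious events. The literal reading of 7.6, under which everyone moves, is an upper bound rather than an expectation, because Appendix 1 schedules full visits from month 9 to month 24. This is a data-collection inconsistency that should be corrected while events can still be recorded. It does not threaten the primary analysis.

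**What to change.** Reconcile 8.2.1 and 8.2.2 with Appendix 2 so that one rule applies, and state in 7.6 which subjects enter reduced follow-up. In section 10, define the AE rate: which events count, the denominator and the period.

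- **If all adverse events are to be collected:** correct the Appendix 2 row and analyze full follow-up. Censoring at the move would then discard valid data.
- **If collection stays restricted:** compute non-serious AE rates only on time under the full schedule, ending at the move. Say that this censoring may be informative, because the reason for moving may be related to AE risk. Report SAEs and severe hypoglycemia over all follow-up.

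In either case, show patient time on each schedule.

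The cost is wording and one derived date per subject. Collecting all events would also mean some added site work at reduced visits. Under the restricted option, the same non-serious events are divided by less time, so the rate and its interval both scale up: by 720/664 = 1.08 if 10% move, and by 720/440 = 1.64 if 50% move. The interval is only slightly wider if few subjects move, and relative precision is unchanged.

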- HbA1c comparing GLASSIA treated versus control CIT-06 subjects at 1 year and 2 years following the *first* and *last* islet transplant(s)

Glycemic Control

- The change in Clarke score from baseline in GLASSIA treated versus control CIT-06 subjects at:
 - 1 year after the first islet transplant.
 - 2 Years after the first islet transplant
- β -score comparing GLASSIA treated versus control CIT-06 subjects at 1 year and 2 years following the *first* and *last* islet transplant(s)
- Glucose variability and hypoglycemia duration derived from the CGMS comparing GLASSIA treated versus control CIT-06 subjects at 1 year and 2 years following the first and last islet transplant(s)
- Basal (fasting) and 90-min glucose and c-peptide derived from the mixed-meal tolerance test (MMTT) comparing GLASSIA treated versus control CIT-06 subjects at 1 year and 2 years following the first and last islet transplant(s)
- MAGE comparing GLASSIA treated versus control CIT-06 subjects at 1 year and 2 years following the first and last islet transplant(s)
- Glycemic lability index (LI) comparing GLASSIA treated versus CIT-06 control subjects at 1 year and 2 years following the first and last islet transplant(s)
- Ryan hypoglycemia severity (HYPO) Score comparing GLASSIA treated versus control CIT-06 subjects at 1 year and 2 years following the first and last islet transplant(s)
- C-peptide: (glucose· creatinine) ratio (CPGCR) comparing GLASSIA treated versus control CIT-06 subjects at 1 year and 2 years following the first and last islet transplant(s)
- Rate of favorable outcome at each center preparing islets (rate of subjects with HbA1c \leq 6.5% and absence of severe hypoglycemic events from Day 28 to Day 730, or reduction in HbA1c of 1 point and absence of severe hypoglycemia from Day 28 to Day 730).

Repeat Transplants

- The proportion of subjects receiving a second islet transplant comparing GLASSIA treated versus control CIT-06 subjects at 1 year and 2 years following the first and last islet transplant(s)
- The proportion of subjects receiving a third islet transplant comparing GLASSIA treated versus control CIT-06 subjects at 1 year and 2 years following the first and last islet transplant(s)

Other Efficacy Endpoints

- Cardiovascular events [death, cerebrovascular accident (CVA), myocardial infarction (MI)] and changes in atherogenic profile for GLASSIA treated versus control subjects at 1 year and 2 years following the first and last islet transplant(s)

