- Renal impact measures including renal allograft survival and function measured by glomerular filtration rate (GFR), serum creatinine (SCr) and urinary albumin creatinine ratio comparing

GLASSIA treated versus control subjects at 1 year and 2 years following the first and last islet transplant(s)

Exploratory Mechanistic Endpoints

- Assessment of the effect of AAT on serum cytokines released in the early post transplant period (1 month) comparing GLASSIA versus control subjects from CIT-06
- Assessment of the effect of AAT on the inflammatory gene transcriptional profile of PBL at day 14 and 75 comparing pre-and post transplant samples
- Correlation of reaching target AAT levels with metabolic outcomes
- Histological survival of subcutaneous islets in subcutaneous auxiliary graft and correlation with overall graft survival

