5.8.2 Modification of Standard Immunosuppression

ISLETS ARE UNSUITABLE

Should an islet product become unsuitable for transplantation subsequent to induction immunosuppression, the subject will remain on maintenance therapy required for their renal transplant. This will provide sufficient time for organ procurement, islet isolation, and infusion of an islet product without any additional induction treatment to the recipient. An emergency request will be placed through UNOS that the next available pancreas for islet transplantation is directed to the selected manufacturing site. When an organ becomes available, investigators should defer to the MOP to determine the amount and type of induction immunosuppression that will be administered at the time of islet transplant.

GRAFT FAILURE

Subjects who experience islet graft failure will be maintained on their current immunosuppressive regimen for their renal graft as long as a subsequent islet transplant is possible. If/when it is determined that a subject will not receive a subsequent islet transplant, the subject will move to the reduced follow-up schedule.

ALLERGIC REACTION TO ATG

If a subject demonstrates an allergic reaction to thymoglobulin that results in cancellation of the initial transplant and the investigators feel that future use of the drug in the subject is contraindicated, the steps outlined should be followed. Once another organ becomes available, the subject will receive the alternate induction immunosuppressive regimen outlined in this protocol.

INTOLERANCE OF PROTOCOL MEDICATIONS

In the event that protocol-regulated concomitant medications are not tolerated, the subject will continue taking the immunosuppressive therapy in order to protect the islet and renal grafts. In the event that the immunosuppression regimen is not tolerated, the site PI may elect to prescribe an alternative immunosuppression regimen. The intent would be for the alternative regimen to be temporary in nature.

where possible and any such decision made with the primary interest of maintaining the function of the renal allograft. Any non-protocol directed study treatment modification that the site PI determines is necessary should be reported as a protocol deviation.

RABBIT ANTI-THYMOCYTE GLOBULIN-INDUCED ANAPHYLAXIS

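### The reduced follow-up schedule (Appendix 2) omits the Clarke survey, urine albumin/creatinine and the lipid profile, although these feed 1- and 2-year endpoints and the subjects stay in the intent-to-treat analysis

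*Combined protocol and SAP*

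**What the plan says.** Section 5.8.3 states that subjects who stop study treatment early "will enter the reduced follow-up schedule outlined in Appendix 2", and then that "Data from these subjects will be used in the intent-to-treat analysis". Section 5.8.2 sends subjects with graft failure the same way once no further transplant is planned: "the subject will move to the reduced follow-up schedule". Section 7.6 adds subjects who do not meet the criteria for another transplant.

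Appendix 2 gives its own purpose: "For the purpose of monitoring safety and efficacy parameters, the subjects should be followed according to the reduced follow-up schedule". Under "ASSESSMENTS FOR ALL SUBJECTS ON REDUCED FOLLOW-UP" it lists five rows: SAEs and hypoglycemic events, alloantibody, HbA1c, serum creatinine, and "QOL questionnaires via mail".

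The endpoints at issue are in Section 4.1.2:
- "The change in Clarke score from baseline in GLASSIA treated versus control CIT-06 subjects at" 1 and 2 years after the first transplant;
- renal "function measured by glomerular filtration rate (GFR), serum creatinine (SCr) and urinary albumin creatinine ratio", at 1 and 2 years after the first and last transplants;
- change in atherogenic profile at the same times. Section 9.1.9 defines this as fasting lipids, CRP and apolipoproteins A1 and B.

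Section 4.1 counts hypoglycemia scores, cardiovascular impact and renal impact among the additional secondary endpoints. Appendix 1 schedules all three measures; Appendix 2 schedules none of them.

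**The concern.** The plan keeps these subjects in the analysis but stops collecting three of the measures to be analysed. Graft failure is one reason for entering Appendix 2, and it plausibly bears on hypoglycemia awareness and metabolic state. The missing values would then tend to come from subjects who did worse. Section 10 gives no missing-data rule. The mixed models in Section 10.1.2 would have no scheduled post-failure values of these measures from which to learn. After graft failure, c-peptide is bounded by the definition of failure, but a Clarke score, an albumin/creatinine ratio or a lipid value cannot be assigned that way. Values not collected at the time cannot be recovered later.

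At stake are the within-cohort change from baseline and the comparison with CIT-06. None of the three measures enters the day-75 primary endpoint.

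**Working it through.** The plan states no figure for this point, so the check is mainly a comparison of schedules, followed by an illustration.

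**1. What is kept and what is lost on Appendix 2**

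| Endpoint component | Appendix 1 | Appendix 2 |
|---|---|---|
| HbA1c | yes | yes |
| Hypoglycemic events | yes | yes |
| Serum creatinine (and so CKD-EPI GFR) | yes | yes |
| Death, MI, CVA | yes | can be captured as SAEs |
| Clarke survey | yes | no |
| Spot urine albumin/creatinine | yes | no |
| Lipids, apolipoproteins, CRP | yes | no |
| QOL | no | yes |

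No endpoint in Section 4.1 or Section 10 uses QOL, and Section 9 describes no QOL instrument.

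**2. When the loss begins.** It begins when the subject moves. Sections 4 and 7.6.2 allow no transplant once 8 months have passed since the first. Under Section 5.8.2, a graft that fails between month 8 and the 1-year visit therefore leads to Appendix 2 before the 1-year measurement. A subject who moves after year 1 keeps the year-1 values and loses only the later ones.

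**3. Illustration for the Clarke score.** All inputs are assumptions: a fraction f of 0.1 to 0.3 is unmeasured, the mean change is g in measured subjects and b in unmeasured ones.

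All-subject mean = (1 − f)·g + f·b. Overstatement = g / (all-subject mean) − 1.

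| f | g = −3, b = 0 | g = −4, b = −1 | g = −3, b = −1 |
|---|---|---|---|
| 0.1 | −2.7; 11% | −3.7; 8% | −2.8; 7% |
| 0.2 | −2.4; 25% | −3.4; 18% | −2.6; 15% |
| 0.3 | −2.1; 43% | −3.1; 29% | −2.4; 25% |

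**4. Comparison with CIT-06.** Assume 10% failures on GLASSIA, 30% in CIT-06, g = −3 and b = 0. The all-subject means are 0.9 × (−3) = −2.7 and 0.7 × (−3) = −2.1, a true advantage of 0.6 points. What is observed depends on who is measured after failure:
- neither cohort: −3.0 against −3.0, difference 0;
- CIT-06 only: −3.0 against −2.1, GLASSIA 0.9 better;
- GLASSIA only: −2.7 against −3.0, GLASSIA 0.3 worse;
- both: −2.7 against −2.1, the true 0.6.

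**5. Precision.** Table 9 rests on all 20 subjects being measured: for the HYPO score, 1.96 × 750/√20 = 328.7, against the stated 329. Table 9 gives no standard deviation for the three measures here, so only relative widening can be stated. With 2 to 6 of 20 unmeasured, half-widths grow by √(20/18) − 1 = 5% to √(20/14) − 1 = 20%.

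**The case against.** A reader might infer that the Clarke, renal and cardiovascular comparisons would be made only in subjects with working grafts. The documents do not support that. Serum creatinine stays on the schedule, and death, MI and CVA can surface as SAEs. Subjects with graft failure move only once a further transplant is ruled out. Entry by discontinuation or under Section 7.6 does not require a failed graft. Late movers keep their year-1 values.

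A second objection is that adding assessments for GLASSIA subjects may damage the comparison. CIT-06 had completed enrollment and passed its 1-year endpoint. Section 4.1 says these measures were collected there, but not whether collection continued after graft failure. If it did not, measuring only the GLASSIA failures creates the reversed case in step 4. This stands, and the fix must allow for it. It does not weaken the case for complete data in the within-cohort analysis of change.

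Third, the stakes are modest. Section 10.1.3 lists the Clarke change among endpoints analysed descriptively, and Section 10.1.2 promises qualifiers on significant secondary findings. The assumed fall of 3 to 4 points also needs high starting scores, whereas inclusion criterion 8 admits subjects on HbA1c alone. Both remarks are fair and limit the weight of the illustration.

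Finally, Appendix 2 also lacks the MMTT, FSIGT, CGMS, insulin dose and the glucose records behind MAGE, LI and HYPO. The change proposed here closes only the part that is cheap to close.

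**Conclusion.** The concern holds in limited form. Appendix 2 does not schedule three measures that feed 1- and 2-year endpoints, although its stated purpose includes efficacy monitoring and Section 5.8.3 puts the data in the intent-to-treat analysis. The resulting missingness is partly outcome-driven and begins when the subject moves.

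The size of the bias cannot be established. The 7-43% range rests wholly on an assumed 10-30% unmeasured and on assumed Clarke changes. It also treats every such subject as missing, so it should not be read as an estimate for this trial. No size can be offered for the urine ratio or lipids. A reader might also infer a direction of bias against CIT-06; the documents do not settle one, because they do not say what CIT-06 measured after graft failure. Nor does the QOL row cause the gap: it shows that the table and the endpoint list do not match.

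**What to change.** - Add the Clarke survey to Appendix 2 at days 365 and 730 after the first infusion, by mail or phone. Section 9.1.4 describes eight questions that the subject answers and the investigator scores.
- Add a first-morning spot urine and a fasting lipid/apolipoprotein/CRP tube to the yearly HbA1c and creatinine draws. Those draws are timed from the final transplant, while the endpoints are also timed from the first, so set the collections to cover both sets of 1- and 2-year dates.
- Use these values in the intent-to-treat pre-post analysis of the GLASSIA cohort.
- Before the comparison with CIT-06, establish whether CIT-06 measured these items after graft failure. If it did not, report the comparison on a like-for-like set in both cohorts, alongside the all-subject GLASSIA estimate.
- Either drop the QOL row or define an endpoint and a baseline for it. This is optional and separate from the gap.

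The cost is one short form, one urine sample and one tube, mostly at contacts that already draw blood. Where the first and final transplants differ, an extra collection may be needed. The downside is slightly more burden for subjects on reduced follow-up.
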